**RO7049389—F. Hoffmann-La Roche Ltd**

Protocol YP39406, Version 4

**RO7049389—F. Hoffmann-La Roche Ltd**  
2/Protocol YP39406, Version 4

## PROTOCOL AMENDMENT, VERSION 4 RATIONALE

Protocol YP39406 has been amended to incorporate the following changes based on the emerging data from this study (YP39406) and the first-in-human (FIH) study (YP39364):

- [REDACTED] The modification to the study design will support characterization of safety, tolerability and PK profiles of RO7049389 in healthy Chinese subjects.
- [REDACTED] The highest dose level to be included in this study will now be based on the observed exposure in the FIH study (YP39364) which has been demonstrated to be safe and well tolerated.

Additional minor changes have been made to correct typographical errors and to improve clarity and consistency. Substantial new information appears in italics. This amendment represents cumulative changes to the original protocol.

**RO7049389—F. Hoffmann-La Roche Ltd**  
3/Protocol YP39406, Version 4

## PROTOCOL AMENDMENT, VERSION 4: SUMMARY OF CHANGES

### PROTOCOL SYNOPSIS

The protocol synopsis has been updated to reflect the changes to the protocol, where applicable.

[figure not shown]
#### 3.1.1 Overview of Study Design

This study will leverage the data which will have been generated in the FIH study, allowing targeted evaluation of fewer doses. ~~In addition, this study proposes to evaluate SAD and MAD of the same total daily dose level in a single subject cohort after approximately 1 week washout. The total daily dose in the MAD part will be equal or lower than the dose used in the SAD part for the same cohort.~~

[...]

**RO7049389—F. Hoffmann-La Roche Ltd**  
4/Protocol YP39406, Version 4

**Figure 1 Overall Study Design and Dose-escalation – new Figure**

Dotted lines indicate optional cohorts. See Table 1 for additional information.

Escalation to the next single dose cohort will be based primarily on the safety and available PK data through 24 hours post-single dose in the previous cohorts. The MAD phase may start after a wash-out period of approximately 1-week, providing that the safety information through 24 hours post-dose in the SAD phase at the same cohort dose level, and available safety information from MAD cohorts in the entry-into-human study (YP39364), have been reviewed.

[....]

**RO7049389—F. Hoffmann-La Roche Ltd**  
5/Protocol YP39406, Version 4

[....]

[....]

H

The

highest dose level *and exposure* to be included in this study will be within the dose *and exposure range* ~~that which~~ has been demonstrated to be safe and well tolerated in FIH Study YP39364.

### **3.1.1.3 Dietary Requirements**

[....]

In the MAD phase (*except cohort 4, which will be in the fasted state*), a **standard breakfast** or dinner will be served to healthy volunteers 30 minutes prior to dosing, which should be consumed within 30 minutes.

[....]

### **3.1.2.1 Dose Escalation Stopping Rules**

[....]

- It is predicted that further dose-escalation will not result in a further increase in plasma exposure.
- The proposed dose *or exposure* exceeds those previously evaluated in the study YP39364.

[....]

**RO7049389—F. Hoffmann-La Roche Ltd**  
6/Protocol YP39406, Version 4

### **3.2.1 Rationale for Dosage Selection**

[....]

Subsequent dose-levels may be adjusted based on the PK, tolerability and safety results from FIH Study YP39364 and available data from current Study YP39406. The highest dose-level *and exposure* to be included in this study will be within the dose range *and exposure* which has been demonstrated to be safe and well tolerated in FIH Study YP39364.

#### **4.3.2.1 RO7049389 and Placebo**

##### **MAD Phase**

[....]

*Except for cohort 4, which will be in the fasted state, a*A standard breakfast or dinner will be served to healthy volunteers 30 minutes prior to dosing, which should be consumed within 30 minutes. RO7049389 or placebo will then be administered.

[....]

**RO7049389—F. Hoffmann-La Roche Ltd**  
12/Protocol YP39406, Version 4

**RO7049389—F. Hoffmann-La Roche Ltd**  
13/Protocol YP39406, Version 4

## PROTOCOL SYNOPSIS

**TITLE:** A RANDOMIZED, SPONSOR-OPEN, INVESTIGATOR-BLINDED, SUBJECT-BLINDED, PLACEBO-CONTROLLED, SINGLE-ASCENDING DOSE (SAD) AND MULTIPLE-ASCENDING DOSE (MAD) STUDY TO INVESTIGATE THE SAFETY, TOLERABILITY, AND PHARMACOKINETICS OF RO7049389 IN HEALTHY CHINESE SUBJECTS

**PROTOCOL NUMBER:** YP39406

**VERSION:** 4

**EUDRACT NUMBER:** N/A

**IND NUMBER:** N/A

**TEST PRODUCT:** RO7049389

**PHASE:** I

**INDICATION:** N/A

**SPONSOR:** F. Hoffmann-La Roche Ltd

**RO7049389—F. Hoffmann-La Roche Ltd**  
14/Protocol YP39406, Version 4

---

## **OBJECTIVES**

The **primary objective** of this study is as follows:

- To assess the safety and tolerability of RO7049389 compared to placebo after single- and multiple-ascending oral doses in healthy Chinese subjects.

The **secondary objective** of this study is as follows:

- To assess the pharmacokinetics (PK) of RO7049389 after single-ascending and multiple-ascending oral doses in healthy Chinese subjects.
- To investigate metabolites (M5, M6, and M11) of RO7049389 in selected plasma samples.

---

## **STUDY DESIGN**

### **Description of Study**

Healthy subjects will be enrolled into one of 3 planned cohorts and one optional cohort. Cohort 1 will include 4 healthy subjects, with 2 randomly assigned to RO7049389 (200mg) and 2 assigned to placebo. From Cohort 2 to Cohort 4, each of the cohorts will include 12 healthy subjects with 10 subjects randomly assigned to RO7049389 and 2 subjects randomly assigned to placebo.

In Cohort 1, subjects will receive one single dose of the assigned study medication. In subsequent cohorts, subjects will receive one single dose of the assigned study medication, followed by a wash out period of approximately 1-week before entering into a MAD phase of the study. Subjects in the MAD cohorts will be from the SAD cohorts after the wash out period, or from new enrollments if there are discontinuations between the SAD phase and MAD phase for reasons other than safety.

Escalation to the next single dose cohort will be based primarily on the safety and available PK data through 24 hours post single dose in the previous cohorts. The MAD phase may start after a wash out period of approximately 1-week, providing that the safety information through 24 hours post dose in the SAD phase at the same dose level, and available safety information from MAD cohorts in the entry-into-human study (YP39364), have been reviewed.

---

## **NUMBER OF STUDY SUBJECTS**

Due to the nature of this study, the actual number of subjects will be determined during the study. This study may require up to 76 subjects, including:

- About 40 healthy subjects to be enrolled in Cohort 1 of 4 subjects and Cohort 2 to Cohort 4 of about 12 subjects each.
- Up to 36 healthy subjects to be enrolled if new subjects are needed for the MAD phase, in case of non-safety related discontinuations between two periods (i.e., replacement subjects),
- For each part, up to two back-up subjects can undergo the preparatory activities in order to replace participants who withdraw from the study for non-safety reasons.

Subjects who drop out of the study for non-safety reasons may be replaced to ensure sufficient data to characterize the safety and PK profile, and to make a dose-escalation decision. Subjects who withdraw from the study due to poor tolerability, or, due to study drug-related adverse events, will not be replaced.

---

## **TARGET POPULATION**

The study will be conducted in Chinese healthy, male and female subjects of non-childbearing potential, 18 to 60 years of age.

---

---

## **INCLUSION/EXCLUSION CRITERIA**

### **Inclusion Criteria**

Study subjects must meet the following criteria for study entry:

1. Chinese healthy male and female subjects, 18 to 60 years of age, inclusive. Healthy status is defined by absence of evidence of any active or chronic disease following a detailed medical and surgical history, a complete physical examination including vital signs, 12-lead ECG, hematology, blood chemistry, serology and urinalysis.
2. A Body Mass Index (BMI) of between 19 to 27 kg/m^2 inclusive, and a body weight of at least 45 kg.
3. Women should be of non-childbearing potential. Female subjects must be either surgically sterile (by means of hysterectomy and/or bilateral oophorectomy) or post-menopausal for at least one year (defined as amenorrhea  $\geq$  12 consecutive months without another cause, and confirmed by follicle stimulating hormone level  $> 35$  mIU/mL).
4. For men: agreement to remain abstinent (refrain from heterosexual intercourse) or use contraceptive measures, and agreement to refrain from donating sperm, as defined below:
  - a. With female partners of childbearing potential, men must remain abstinent or use two methods of contraception with their partner, one of which must be a barrier method (i.e., condom), for the duration of the study and for at least 28 days after the last dose of study drug to avoid exposing the embryo. Men must refrain from donating sperm during this same period.
  - b. The reliability of sexual abstinence should be evaluated in relation to the duration of the clinical trial and the preferred and usual lifestyle of the patient. Periodic abstinence (e.g., calendar, ovulation, symptothermal, or post-ovulation methods) and withdrawal are not acceptable methods of contraception.
  - c. Other acceptable forms of contraception for this study include vasectomy, bilateral tubal occlusion, intrauterine device (IUD) or proper use of hormonal contraceptives.
5. Informed of, willing and able to comply with all of the protocol requirements and the investigational nature of the study, and have signed an informed consent form (ICF) in accordance with institutional and regulatory requirements.

### **Exclusion Criteria**

Study subjects who meet any of the following criteria will be excluded from study entry:

1. Pregnant (positive pregnancy test) or lactating women, and male subjects with partners who are pregnant or lactating.
2. History or symptoms of any clinically significant gastrointestinal, renal, hepatic, broncho-pulmonary, neurological, psychiatric, cardio-vascular, endocrinological, hematological or allergic disease, metabolic disorder, cancer or cirrhosis.
3. Personal history of congenital long QT syndrome or family history of sudden death.
4. History of Gilbert's syndrome.
5. History of having received or currently receiving any systemic anti-neoplastic (including radiation) or immune-modulatory treatment (including systemic oral or inhaled corticosteroids)  $\leq$  6 months prior to the first dose of study drug or the expectation that such treatment will be needed at any time during the study.
6. Subjects who have had significant acute infection, e.g., influenza, local infection, acute

---

**RO7049389—F. Hoffmann-La Roche Ltd**

16/Protocol YP39406, Version 4

---

gastrointestinal symptoms or any other clinically significant illness within two weeks of dose administration.

7. Any confirmed significant allergic reactions (urticaria or anaphylaxis) against any drug, or multiple drug allergies (non-active hay fever is acceptable).
8. Any clinically significant concomitant diseases or condition that could interfere with, or treatment of which might interfere with, the conduct of the study, or that would, in the opinion of the Investigator, pose an unacceptable risk to the subject in this study.
9. Confirmed (based on the average of three separate resting blood pressure measurements, properly measured with well-maintained equipment, after at least 10 minutes rest) systolic BP greater than 140 or less than 90 mmHg, and diastolic BP greater than 90 or less than 50 mmHg at screening.
10. Clinically relevant ECG abnormalities on screening ECG, e.g.,
  - a. QTcF > 450 msec or < 300 msec
  - b. Notable resting bradycardia (HR < 45 bpm), or HR > 90 bpm.
  - c. ECGs with documented machine errors in the interval duration assessments
  - d. Evidence of atrial fibrillation, atrial flutter, complete bundle branch block, Wolf-Parkinson-White Syndrome, or cardiac pacemaker.
11. ECG with QRS and/or T-wave judged to be unfavorable for a consistently accurate QT measurement (e.g., neuromuscular artifact that cannot be readily eliminated, arrhythmias, indistinct QTS onset, low amplitude T-wave, merged T- and U-waves, prominent U-waves).
12. Creatinine clearance (CrCl) ≤ 70 mL/min (using the Cockcroft-Gault formula).
13. Positive test at screening of any of the following: hepatitis A (HAV IgM Ab), hepatitis B (HBsAg), hepatitis C (HCV RNA or HCV Ab) or human immunodeficiency virus 1 and 2 (HIV Ab).
14. Any other clinically significant abnormalities in laboratory test results at screening. In the case of uncertain or questionable results, tests performed during screening may be repeated before randomization to confirm eligibility.
15. Participation in an investigational drug or device study within 90 days prior to screening or more than 4 times per year.
16. Donation or loss of blood over 500 mL within 3 months prior to screening.
17. Positive test for drugs of abuse (including recreational drugs) and/or positive alcohol test at screening or on Day -1.
18. Any suspicion or history of drug and/or alcohol abuse within the last year.
19. History (within 3 months of screening) of alcohol consumption exceeding two standard drinks per day on average (1 standard drink = 10 grams of alcohol). Alcohol consumption will be prohibited at least 48 hours before screening, 48 hours before and 48 hours after each dose, and 48 hours before each scheduled visit.
20. Use of > 5 cigarettes or equivalent nicotine-containing product per day.
21. Taking any prescribed or over-the-counter medications (including vitamins or herbal remedies) within 2 weeks of first dosing or within 5 times the elimination half-life of the medication prior to first dosing (whichever is longer). Occasional acetaminophen/paracetamol is allowed. Exceptions may be made on a case-by-case basis following discussion and agreement between the Investigator and the Sponsor.
22. Subjects under judicial supervision, guardianship or curatorship.
23. Medical or social conditions that would potentially interfere with the subject's ability to comply with the study visit schedule or the study assessments

---

**RO7049389—F. Hoffmann-La Roche Ltd**

17/Protocol YP39406, Version 4

---

### **LENGTH OF STUDY**

The total duration of the SAD part of the study will be approximately 8 weeks (from screening through study completion) for each randomized subject as follows:

- Screening: Up to 4 weeks
- In clinic period: Days –1 to 3
- Ambulatory visits: Days 4, 5, 8
- Safety Follow-up Call: Day 29

The total duration of the MAD part of the study will be approximately 10 weeks\* (from screening through study completion) for each randomized subject as follows:

- Screening: Up to 4 weeks
- In Clinic period: Day -1 to Day 16
- Safety Follow-up Visit: Day 21
- Safety Follow-up Call: Day 42

\*For subjects who previously participated in the SAD part of the study, their total duration in the study will be approximately 12 weeks: up to 4 weeks screening for SAD, approximately 1 week treatment on SAD, approximately 1 week washout, and 6 weeks for MAD (no additional screening visit).

---

### **END OF STUDY**

The end of the study is defined as the date when the last study subject last observation (LSLO) occurs. LSLO is expected to occur 28 days after the last dose is administered.

---

### **OUTCOME MEASURES**

#### **SAFETY OUTCOME MEASURES**

The safety outcome measures for this study are as follows:

- Incidence and severity of adverse events.
- Incidence of laboratory abnormalities, based on hematology, clinical chemistry, coagulation, and urinalysis test results.
- ECGs.
- Vital signs including blood pressure (BP), pulse rate and body temperature.

#### **PHARMACOKINETIC OUTCOME MEASURES**

The pharmacokinetic outcome measures for this study are as follows:

##### **PK parameters (SAD)**

- $C_{max}$ : Maximum observed plasma concentration
- $T_{max}$ : Time to maximum observed plasma concentration
- $AUC_{0\text{-last}}$ : Area under the plasma concentration versus time curve up to the last measurable concentration
- $AUC_{0\text{-inf}}$ : Area under the plasma concentration versus time curve extrapolated to infinity
- $T_{1/2}$ : Apparent terminal phase half-life
- $CL/F$ : Apparent clearance after oral administration

##### **PK parameters (MAD)**

- $C_{max}$ : Maximum observed plasma concentration after single dose and at steady-state
- $T_{max}$ : Time to maximum observed plasma concentration after single-dose and at steady-state

**RO7049389—F. Hoffmann-La Roche Ltd**

18/Protocol YP39406, Version 4

- $C_{trough}$ : Trough plasma concentration
- $AUC_{0-t}$ : Area under the plasma concentration-time curve for a dosing interval after single dose and at steady-state
- $T_{1/2}$ : Apparent terminal phase half-life after single-dose and at steady-state
- Accumulation index of RO7049389

#### **PK parameters (SAD and MAD):**

Plasma samples collected in the study will be qualitatively and/or quantitatively analyzed for the metabolites (M5, M6, and M11) of RO7049389 in selected samples.

---

#### **INVESTIGATIONAL MEDICINAL PRODUCT(S)**

The investigational medicinal product in this study are:

RO7049389 and placebo, which will be supplied and packaged by the Sponsor. [REDACTED]

[REDACTED] A matching-placebo, in terms of size, shape and color, has also been developed for clinical usage.

---

#### **PROCEDURES**

Schedules of Assessments (SoA) are provided in Appendices 1-4.

---

#### **STATISTICAL METHODS**

#### **SAFETY ANALYSES**

All study subjects who have received at least one dose of the study medication (RO7049389 or matching placebo), whether prematurely withdrawn from the study or not, and with at least one safety assessment, will be included in the safety analysis. The safety data, including AEs, reasons for withdrawal from study, laboratory data, ECG, concomitant medications, vital signs, and physical examination results will be listed and summarized descriptively. Laboratory test values will be presented by individual listings with flagging of values outside the normal ranges.

#### **PHARMACOKINETIC ANALYSES**

Study subjects will be excluded from the pharmacokinetic analysis population if they significantly violate the inclusion or exclusion criteria, deviate significantly from the protocol or if data are unavailable or incomplete which may influence the pharmacokinetic analysis. Excluded cases will be documented together with the reason for exclusion. All decisions on exclusions from the analysis will be made prior to database closure. Non-compartmental analysis will be employed for estimation of PK parameters. All PK parameters will be presented by individual listings and summary statistics for each cohort including means, geometric means, medians, ranges, standard deviations and coefficients of variation. Plasma samples collected in the study will be qualitatively and/or quantitatively analyzed for the presence of metabolites of RO7049389. A population PK model development and analysis may be performed. The Population PK results will be reported in a separated document.

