### **3.1.2 Dose-Escalation Decision Criteria**

A Safety Review of the data will be conducted by the Principal Investigator, the Medical Monitor, and the Sponsor Clinical Team prior to each RO7049389 dose-escalation.

Escalation to the next dose cohort will be based primarily on the safety and tolerability information (including adverse events [AEs], electrocardiograms [ECGs], vital signs, clinical laboratory test results) up to 48 hours post-dose (SAD), and secondarily on all available PK data up to 24 hours post-dose (SAD) in a minimum of 8 subjects (receiving active study drug or placebo) within the previous cohort. Doses will be escalated by three-fold increments but for higher doses the increments will be smaller than three-fold. The decision to escalate the dose will be made by mutual agreement between the Sponsor and the Investigator.

The MAD phase (Cohorts 2, 3, and 4) can begin after a washout period of at least one week, and once safety and tolerability information through 24 hours post-dose in the SAD phase (see [Figure 1](#)), and available safety and tolerability information from MAD cohorts in the entry-into-human study (YP39364) have been reviewed. Additionally, both the Sponsor and the Investigator must agree that the safety data can support continuing with the multiple-dose phase.

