#### **4.2 METHOD OF TREATMENT ASSIGNMENT AND BLINDING**

##### **4.2.1 Method of Blinding**

Randomization numbers will be generated by the Sponsor or its designee.

The study is Investigator-blinded and Subject-blinded. In order to minimize bias in reporting, collecting, and interpreting safety data. Study subjects, Investigator(s), and all individuals in direct contact with study subjects at the investigative site will remain blinded until the completion of the study, except the pharmacist handling the study drug distribution.

The study is Sponsor-open. At the Sponsor side, the Clinical Pharmacologists, the Study Pharmacometrist, the Study Clinical Pharmacology Scientist, the Study Biostatistician, the Statistical Programmer/Data Acquisition Specialist/Clinical Data Programmer, and the individual responsible for PK sample bioanalysis – members of the Sponsor's project and study teams who do not have direct contact with the subjects – will be unblinded to

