### **6.3.2 Pharmacokinetic Analysis Population**

Study subjects will be excluded from the pharmacokinetic analysis population if they significantly violate the inclusion or exclusion criteria, deviate significantly from the protocol or if data are unavailable or incomplete which may influence the pharmacokinetic analysis. Excluded cases will be documented together with the reason for exclusion. All decisions on exclusions from the analysis will be made prior to database closure.

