## **6.6 PHARMACOKINETIC ANALYSES**

Non-compartmental analysis will be employed for estimation of PK parameters.

Individual plasma concentrations at each sampling time-point for RO7049389 of each cohort will be presented by listings and appropriate descriptive summary statistics, including means, medians, geometric means, ranges, standard deviations and coefficients of variation. Individual and mean plasma concentration of each cohort versus time data will be plotted on semi-logarithmic scales.

All PK parameters will be presented by individual listings and summary statistics for each cohort including means, geometric means, medians, ranges, standard deviations and coefficients of variation.

The relationship of selected PK parameters from Day 1 with dose will be evaluated graphically to establish dose-linearity. Dose-proportionality may be assessed by estimating the slope of the linear regression of logarithmically transformed variables  $C_{\max}$ ,  $AUC_{0-\text{last}}$  and  $AUC_{0-\infty}$  versus the logarithmically transformed dose. A 95% confidence interval for the slope which includes the value 1 would be consistent with dose-proportionality.

Plasma samples collected in the study will be qualitatively and/or quantitatively analyzed for the presence of metabolites of RO7049389.

A population PK model development and analysis may be performed. The Population PK results will be reported in a separated document.

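### PK exclusions are judgement calls due only by database closure, which in this sponsor-open study does not ensure they are made without knowledge of the concentrations

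*Combined protocol and SAP*

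**What the plan says.** Section 6.3.2, repeated in the synopsis, says that subjects will be "excluded from the pharmacokinetic analysis population if they significantly violate the inclusion or exclusion criteria, deviate significantly from the protocol". The third ground is missing or incomplete data that might affect the analysis. No thresholds or list of qualifying deviations are given. Two safeguards follow: "Excluded cases will be documented together with the reason for exclusion" and "All decisions on exclusions from the analysis will be made prior to database closure".

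Section 4.2.1 makes the study sponsor-open. The roles unblinded to treatment include the clinical pharmacologists, the pharmacometrist, "the Study Biostatistician, the Statistical Programmer/Data Acquisition Specialist/Clinical Data Programmer, and the individual responsible for PK sample bioanalysis". Under Section 3.1.2, escalation rests primarily on safety and "secondarily on all available PK data up to 24 hours post-dose (SAD) in a minimum of 8 subjects" of the previous cohort. Section 4.2.1 adds that individual safety and available PK data go to the Safety Review Meeting in a blinded fashion. Section 3.1.2.1 adds an internal review of unblinded data before each escalation, with Clinical Pharmacology and Biostatistics taking part.

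Section 6.6 plans individual listings and summary statistics for all PK parameters. It also plans an optional regression of log exposure on log dose, read as follows: "A 95% confidence interval for the slope which includes the value 1 would be consistent with dose-proportionality".

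**The concern.** A deadline before database closure guards against outcome-driven exclusions only while the outcome is unknown to whoever decides. That works when the data stay hidden until closure. Here the design opens them earlier, for legitimate escalation reasons, and the exclusion rule was not adapted to that. A subject with an unusual profile and a debatable deviation could be dropped or kept with the concentrations in view, and the plan has no analysis that would show the difference.

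At stake are the exposure summaries behind the secondary objective and the dose-proportionality slope, if it is estimated. Sections 1.3.1 and 3.2.2 say that the data will help to evaluate differences between Chinese and non-Chinese subjects and guide later studies. The groups are small enough for one subject to matter, most of all at 200 mg.

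**Working it through.** **No figure in the plan to reproduce on this point.** The only probability stated is the 94% chance of seeing an adverse event of 25% incidence among 10 subjects. It reproduces (1 − 0.75^10 = 0.944) but has no bearing here.

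**Inputs from the documents.** Active subjects: 2 in Cohort 1 and 10 in each of Cohorts 2 to 4 (Section 3.1.1). Single doses: 200, 400, 600 and 800 mg, with Cohort 4 optional (Table 1). Criterion: the 95% CI for the log-log slope includes 1 (Section 6.6).

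**Assumptions.** One subject is 2-fold or 3-fold away from the others. The true slope is 1 unless stated. The between-subject CV is 20-60%, because the documents give none.

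**1. Geometric mean.** With n subjects, one of them k-fold high, dropping that subject lowers the geometric mean by 1 − k^(−1/n). Dropping a subject k-fold low raises it by k^(1/n) − 1. The two formulas are not interchangeable.

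| n active | k | drop a high subject | drop a low subject |
|---|---|---|---|
| 10 | 2 | −6.7% | +7.2% |
| 10 | 3 | −10.4% | +11.6% |
| 2 | 2 | −29.3% | +41.4% |
| 2 | 3 | −42.3% | +73.2% |

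**2. Leverage at 200 mg.** Let x = ln(dose), d = x(200 mg) − mean(x), and Sxx = the sum of squared deviations of x. Leverage is 1/N + d²/Sxx.
- Three cohorts (N = 22): d = −0.814, Sxx = 2.281, leverage = 0.045 + 0.291 = 0.336. Other subjects: 0.052-0.081.
- Four cohorts (N = 32): d = −0.993, Sxx = 4.530, leverage = 0.031 + 0.218 = 0.249. Other subjects: 0.034-0.065.

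**3. Point slope.** With one 200 mg subject k-fold high and no other noise, slope = 1 + d·ln(k)/Sxx.
- Three cohorts: 1 − 0.814 × 0.693/2.281 = 0.75 for k = 2, and 1 − 0.814 × 1.099/2.281 = 0.61 for k = 3.
- Four cohorts: 1 − 0.993 × 0.693/4.530 = 0.85, and 1 − 0.993 × 1.099/4.530 = 0.76.
- Without that subject, the slope is 1.00 in every case.

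**4. The CI criterion.** The log SD is √ln(1 + CV²), and the half-width is t × SD/√Sxx. At CV 30% and 50%, the half-width is 0.41 and 0.65 with three cohorts, and 0.28 and 0.45 with four. The shifts in step 3 are 0.25 (0.39) with three cohorts and 0.15 (0.24) with four. They lie inside the interval at these CVs, so the conclusion usually survives.

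Simulating the same example at CV 30-50%, dropping the 2-fold subject changes the conclusion in about 8-17% of trials. Dropping the 3-fold subject changes it in about 17-32% (three cohorts) or 14-28% (four). At CV 20% the 3-fold case reaches about 50%.

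**5. Upper bound.** A second simulation (4,000 trials per setting, no planted outlier) asked whether dropping any single subject would switch the conclusion. With true slope 1 this was possible in 12-13% of trials (four cohorts) or 14-15% (three). Over true slopes 1.0-2.0 and CV 20-60%, the maximum is about 41% (four) or 47% (three). It is near zero when the slope is far from 1 and the CV is low. Where the full-data interval excluded 1 (slope 1.25-1.5, CV 30-50%), some one exclusion brought 1 back inside in 14-60% (four) or 46-78% (three) of those trials. All these figures take the most influential subject, whether or not there would be grounds to exclude that subject.

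**The case against.** The strongest reply is that the plan is more open than the timing sentence suggests. Each exclusion is recorded with its reason, protocol deviations are listed and evaluated for impact (Section 6.2), individual PK data are listed (Section 6.6), and nothing may be excluded after closure. A reader could infer that the rule gives no protection at all; the documents do not support that. What stands against the reply is narrower: these measures disclose an exclusion, but they do not make it outcome-blind or show its effect.

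A reader might also infer that the people deciding exclusions have seen every subject's concentrations. The documents do not say so. They name no decider. Escalation uses available PK in a minimum of 8 subjects, the last cohort precedes no further escalation, and entry to the multiple-dose phase requires safety review, not PK. The meeting review is blinded, although blinding to treatment does not in itself hide a concentration. Prior knowledge is a reasonable inference because the unblinded roles cover PK, statistics and bioanalysis; it is not a stated fact.

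It is fair, too, that the slope analysis is optional, all analyses are descriptive, and no formal ethnic comparison is specified. That limits the weight of the point. It does not remove it, because descriptive geometric means also move with exclusions.

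**Conclusion.** The point holds in limited form. The exclusion criteria are judgemental, and the timing rule does not ensure that they are applied without knowledge of the concentrations. No planned analysis would show the effect of an exclusion.

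For one subject 2-fold (3-fold) high, dropping that subject moves a 10-subject geometric mean by about 7% (10%), which is modest, and the 200 mg mean by 29% (42%). The slope is sensitive because only two active subjects sit at the lowest dose. The claim that one exclusion reverses the dose-proportionality result goes too far: reversal is possible, but at CV 30-50% the planted-outlier example leaves the CI conclusion unchanged in most simulated trials.

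All these sizes rest on assumed fold-deviations, and the reversal frequencies also on assumed CVs and slopes. The point concerns the secondary PK results only; the primary safety analysis uses a different population (Section 6.3.1).

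**What to change.** Amend the PK population text in the synopsis and Section 6.3.2, with a matching line in Section 6.6:

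- **(a) With and without.** Report the PK summaries, and any dose-proportionality slope with its 95% CI, twice: with the exclusions applied, and with every active subject who has a calculable parameter.
- **(b) Numeric limits.** For exclusions that need the profile, such as a measurable pre-dose concentration or missing samples around Cmax, fix numeric limits before first dosing. For any cohort already dosed when the change is made, date the limits and rely on (a).
- **(c) Deviation-based exclusions.** Name who decides. Where feasible, decide from the deviation log without reference to the concentrations, and keep a dated record.

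Item (c) is qualified because escalation needs PK quickly and deviations can surface late, so a strict barrier before each cohort's PK release may not be workable. Items (a) and (b) do most of the work.

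The cost is protocol wording, a dated record and one repeated set of PK tables, with no extra data. The downside is that odd profiles without a qualifying reason stay in the main summary and may widen the CV.
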